5.4 Intervention

5.4.1 Experimental arm (phytosomal curcumin)

Phytosomal curcumin Meriva® (Indena S.p.A. Milan, Italy) 1,000 mg (active experimental group)(Indena s.p.a., Milan, Italy) was supplied was administered before meals at a dose of 1000 mg twice daily 12 hours apart (total daily dose: phytosomal curcumin Meriva 2000 mg, corresponding to 400 mg curcuminoids).

Participants were encouraged to take phytosomal curcumin at the same time each day, according to the most convenient time for them. All tablets were produced and sponsored by the manufacturer who otherwise had no role in the study design, data collection, data analysis, data interpretation or publication of this manuscript. Placebo and Meriva® tablets contained the same ingredients except for curcuminoids. For simplicity, Phytosomal curcumin tablets will be referred to as curcumin in the following. Compliance will be considered acceptable if more than 75% of dosages will be ingested. Participants reported missed dosages, concomitant medication, and adverse events during the trial.

5.4.2 Phytosomal curcumin-placebo (inactive, placebo-control group)

Phytosomal curcumin-placebo (Indena S.p.A. Milan, Italy)) consist of identically appearing , colourless, tasteless pills packaged and administered in an identical manner to the active comparator,. Placebo pills and active comparator have identical composition, except for the active phytosomal curcumin substance.

5.4.3 Concomitant therapy and medications

No dose reductions of phytosomal curcumin or placebo will be allowed throughout the 72-week treatment period. Previous treatment with oral antidiabetic drugs (metformin, sulfonylureas, insulin, DPP-IV inhibitors) was continued at the same dose in participants with T2DM at randomisation. The reported rate of hypoglycaemia in literature, with phytosomal curcumin is very low and not different from placebo^{3,4}.

However In the event of recurrent major hypoglycaemic episodes (requiring medical or hospital intervention), the dose of the sulfonylurea will be reduced by 50% at the discretion of the investigators. In the event of recurrent major hypoglycaemic episodes in which no dose reduction could be undertaken (ie, not on a sulfonylurea) the participant will be withdrawn from treatment at the discretion of the chief investigator.

Glycaemic control will be assessed at each 12-weekly trial visit with self-measured plasma glucose readings and HbA1c. In the event that glycaemic control deteriorates, defined as HbA1c >9% (75 mmol/mol), the participant will be informed and counselled with regard to starting open labelled long-acting insulin detemir once daily (Levemir) or other allowed drugs in accordance with European guidelines (<http://www.ema.europa.eu>) to ensure that the participant's standard of diabetes care is not significantly compromised as a result of participating in the clinical trial.

The HbA1c cut-off >9% was based on the opinions of the TMG (GM and RG), consisting of expert endocrinologists and in accordance with previous clinical trial guidance²⁹.

In addition to study medications, participants will receive standard National Health Services (NHS) care recommendations concerning life-style modifications (ie, exercise, weight loss and dietary modification) and management of various coexisting illnesses throughout the trial.

Patients will be asked to limit alcohol consumption to less than 20 mg/day for women (ie, 14 units/week) and 30 mg/day for men (ie, 21 units/week), consistent with current guidelines³⁰

Participants will not be allowed any new prescription or over-the-counter therapies (ie, herbal remedies, milk thistle) that may improve or worsen NASH throughout the duration of the trial, including nutraceuticals of any type containing curcumin.

Potential NASH therapies that will not be allowed during the trial duration included thiazolidinediones (TZDs), GLP-1 receptor agonists, SGLT2 inhibitors, vitamin E, orlistat or other experimental therapies for NASH. Steroids (oral or intravenous), methotrexate and/or amiodarone will also not be permitted based on their ability to promote hepatic steatosis.

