5.2 Inclusion criteria

The trial entry criteria will be based on a diagnosis of 'definite' NASH on liver biopsy obtained within 6 months of screening. Throughout the study, all liver biopsies will be read centrally by one single (RP) expertised pathologist from the central trial site (HUMANITAS Gradenigo), blinded to clinical and laboratory data and to treatment allocation: prior to randomisation, the liver histopathologist will review all of the liver biopsies of the potential participants to assess whether a diagnosis of 'definite' NASH is present.

A 'definite' diagnosis of NASH is defined if all of the following are present on biopsy: (1) macrovesicular steatosis (>5%); (2) hepatocyte ballooning (\pm Mallory Hyaline) and (3) lobular inflammation (mixed infiltrate, related to foci of ballooning). Only patients with 'definite' NASH will be classified as eligible. All participants are to be ≥ 18 to <70 years of age and have a BMI ≥ 25 kg/m² at screening. Patients with type 2 diabetes mellitus (T2DM) at screening had to have stable glycaemic control (HbA1c <9%) and be managed by either diet and/or a stable dose of metformin/sulfonylurea/s. Patients without a history of T2D prior to the screening visit will undergo a 75-g standard OGTT and/or have their HbA1c measured at screening to determine their glycaemic status and will be labelled as 'non-diabetic' if one or more of the following was confirmed

- Impaired fasting glucose, defined using the European Criteria between 110 and 126 mg/dL.
- IGT, defined as 2 h plasma glucose levels between 140 and 200 mg/dL on the 75 g OGTT.
- Normal Fasting Plasma Glucose <110 mg/dL and normal 2 h plasma glucose levels <140 on the 75 g OGTT.
- HbA1c <6.5%

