11. Average alcohol consumption >20 g/d(males) and >10 g/d(females) (as assessed by a validated questionnaire within the last 5 years).
12. Medical/surgery history of; gastric bypass surgery, orthotopic liver transplant (OLT) or listed for OLT, hepatocellular, pancreatic, thyroid carcinoma, acute or chronic pancreatitis and total parenteral nutrition within 6 months of randomisation.
13. Diagnosis of malignancy within the last 3 years (with the exception of treated skin malignancies).
14. Hepatocellular carcinoma: dysplastic or intermediate nodules to be excluded. Regenerative and other nodules to be included at the discretion of the chief investigator.
15. Alanine aminotransferase or aspartate aminotransferase >10×upper limit of normal.

16. >5% weight loss since the diagnostic liver biopsy was obtained.
17. Recent (within 3 months of the diagnostic liver biopsy or screening visit) or significant change (as judged by the chief investigator) in dose of the following drugs: inducers of hepatic steatosis (steroids (oral/intravenous), methotrexate, amiodarone), orlistat and/or multivitamins/vitamin E (containing >200% recommended daily amount; >30 mg/day).
18. Known positivity for antibody to HIV.
19. Currently being treated with renal replacement therapy (ie, haemodialysis or peritoneal dialysis).

Specific exclusion criteria for participants with T2D

1. Participants receiving thiazolidinediones (TZDs), GLP-1-based therapies, SGLT2 inhibitors
3. HbA1c $\geq 10\%$.

Patients who met any of the criteria (listed above) at the screening visit were excluded from trial participation.

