Both active treatment (phytosomal curcumin) and placebo control will be packaged and labelled with a unique identification number (in keeping with the European Unions Good Manufacturing Practice for Medicinal Product guidelines) by the manufacturer (Indena S.p.A.), to the extent that the receiving trial site will be blinded to the study drug throughout the duration of the trial. Sealed parcels (containing electronic information) will be sent with each drug package for the attention of the unblinded members of the central trial management group (TMG) nominated statistician, RG and database programmer, EP, to ensure (1) safe delivery of the correct drug and (2) blinding of the treatment allocation from the remainder of the TMG and the trial patient. Unblinding of treatment will only take place if the identity of the allocated study medication will be necessary for patient safety and care. If a serious adverse event (SAE) is deemed unexpected and possibly, probably or definitely related to phytosomal curcumin (ie, suspected unexpected serious adverse reaction=SUSAR), a clinical member of the TMG was unblinded to the medication to evaluate causality and subsequently label the event either as an unrelated SAE (for patients receiving placebo) or a SUSAR (for patients receiving phytosomal curcumin). The latter will be reported to the MHRA and the NRES, and only if patient safety is jeopardised the study medication will be discontinued and the treating clinician/patient informed.

6. Trial schedule and data collection

The trial will involve nine patient-related visits at their nearest trial site (**Figure 1**).

The study comprises four stages: (1) screening, enrollment, randomisation and baseline investigations (visits 1 and 2, over a maximum period of 14 days), (2) 504 days of study treatment (visits 3–7, over 72 weeks), (3) primary endpoint assessment including liver biopsy (visit 8, within 1 day of the EOT) and (4) post-treatment follow-up assessment (visit 9, 12 weeks after EOT). If the trial investigating team or the trial participant suspected an AE, an unscheduled visit was arranged within 24 h. Each visit included patient interview, clinical examination, anthropometry and blood/urine chemistry.

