with Hank's balanced salt solution, and reconstituted to a concentration of 4×10^5 cells/mL in Hank's balanced salt solution. This method yields > 95% pure PMN and MNC suspensions(56).

NF-kBp50/p65 transcription factor assay kit was purchased from Cayman Chemical (Ann Arbor MI, USA). The method detects specific transcription factor DNA binding activity in nuclear extracts and cell lysates. A specific double stranded DNA sequence containing the NF-kB response element is immobilized onto the bottom of wells of a 96 well-plate. NF-kB in nuclear or cytoplasmatic extract binds specifically to the NF-kB response element. NF-kBp50/65 is detected by addition of specific primary antibody directed against NF-kBp50/65. A secondary antibody conjugated to Horseradish peroxidase is added to provide a sensitive colorimetric readout at 450 nm.

Other clinical and laboratory data

Fasting blood samples will be analysed for full blood count, urea, creatinine and electrolytes, thyroid stimulating hormone (TSH), lipid profile (total cholesterol, high density lipoprotein, triglycerides), liver function tests, prothrombin time, international normalised ratio (INR), amylase, α -fetoprotein, C reactive protein, HbA1c, Monocyte chemoattractant protein-1(MCP-1), and plasma glucose using standard laboratory methods (Roche Modular system, Roche Ltd, Lewes, UK). Urinary albumin excretion rate will be measured using standard routine methods.

Serum Insulin (Merckodia, Uppsala, Sweden), nonesterified fatty acids (Zen-Bio, Research Triangle Park, North Carolina, USA) and CK-18 M30 (M30 Apoptosense ELISA Kit; PEVIVA AB, Bromma, Sweden) lumican and adiponectin will be measured in-house using commercially available colorimetric ELISAs.

Serum caspase-cleaved cytokeratin-18 (CK-18 M30) was performed at study entry to assess hepatic apoptosis. HOMA-IR, a marker of insulin resistance, was calculated in the standard fashion: $\text{glucose} \times \text{insulin} / 22.5$. Measurements of weight (kg), height, systolic/diastolic blood pressure and waist:hip circumferences were recorded. Waist and hip circumferences were defined as

the circumferential measurements immediately above the level of the iliac crests and at the level of the greater trochanters, respectively. BMI was defined as weight in kilograms divided by the square of the height in metres (kg/m²).

Nuclear Factor(NF)- κ B activation in mononuclear cells (MNCs)

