Oxidized LDLs measurement. LDL-conjugated dienes will be determined during the fat load test, as follows. Capillary electrophoresis will be performed as described by Stocks and Miller. The cathode and anode electrolytes and the capillary run buffer will be 40 mM methylglucamine-Tricine, pH 9.0. LDL samples will be injected by low pressure for 4 seconds. Dimethylformamide will be injected as an electroosmotic flow marker for 1 second. A voltage of 24 kV was applied ramping over 0.8 minutes. Migration of LDL particles will be monitored at 200 and 234 nm. The amount of conjugated dienes will be obtained from the percentage of the height of LDL peak at 234 nm related to the height of LDL peak at 200 nm.

ORAL GLUCOSE TOLERANCE TEST (OGTT). Within 3 months from entry into the trial, patients will undergo a standard 75-g oral-glucose-tolerance test (OGTT), with measurement of plasma glucose, insulin, C-peptide, FFA. Areas under the concentration curves (AUCs) of different parameters during the OGTT will be calculated with the trapezoidal method.

The following parameters will be calculated:

Whole body insulin sensitivity. Prehepatic insulin delivery will be estimated as the suprabasal (D) 30-min AUC of C-peptide divided by the 30-min increase in plasma glucose. The hepatic insulin extraction, as a percentage of secreted hormone, will be estimated by $[1 - \frac{\text{AUC insulin}}{\text{AUC C-peptide}}]$. Two indexes of insulin sensitivity will be calculated: the conventional quantitative insulin-sensitivity check index (QUICKI) and oral glucose insulin sensitivity (OGIS), an OGTT-derived index of whole-body insulin sensitivity⁶⁸.

Adipose tissue insulin resistance. Adipose tissue insulin resistance will be calculated (adipose IR = fasting FFA x fasting plasma insulin), as previously described and validated in diabetic and nondiabetic subjects⁶⁹.

70.

Hepatic and muscle insulin resistance. The hepatic and muscle insulin resistance index will be calculated from OGTT as proposed and validated against clamp in nondiabetic subjects⁷¹

Hepatic insulin extraction. The hepatic insulin extraction (He), as a percentage of secreted hormone, will be estimated using the formula $[1-(\text{AUC insulin}/\text{AUC C-pep})]$.

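### Sections 5.2 and 5.4.3 of the protocol disagree on whether patients taking insulin or DPP-IV inhibitors may enter, and the hypoglycaemia rule in 5.4.3 does not fit the insulin use that the same section permits

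*Protocol*

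**What the plan says.** Four parts of the protocol bear on background diabetes treatment.

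- **Section 5.2 (inclusion).** Besides an HbA1c limit, patients with type 2 diabetes at screening had to "be managed by either diet and/or a stable dose of metformin/sulfonylurea/s". No other drug class is listed.
- **Section 5.3 (Box 1, diabetes-specific exclusions).** The drug exclusion reads "Participants receiving thiazolidinediones (TZDs), GLP-1-based therapies, SGLT2 inhibitors". Insulin and DPP-IV inhibitors do not appear.
- **Section 5.4.3 (background treatment).** "Previous treatment with oral antidiabetic drugs (metformin, sulfonylureas, insulin, DPP-IV inhibitors) was continued at the same dose in participants with T2DM at randomisation".
- **Section 5.4.3 (treatment during the trial).** If HbA1c rises above 9%, the participant is to be "counselled with regard to starting open labelled long-acting insulin detemir once daily", or other allowed drugs. For recurrent major hypoglycaemia, the sulfonylurea dose may be halved at the investigators' discretion. The other branch covers "recurrent major hypoglycaemic episodes in which no dose reduction could be undertaken (ie, not on a sulfonylurea) the participant will be withdrawn from treatment", and the sentence goes on to leave that withdrawal to the chief investigator's discretion.

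**The concern.** An entry criterion and a concomitant-treatment rule should describe the same population. Here one section leaves out a group of patients whose treatment another section says was carried on. Two sites, or one site on two occasions, could treat the same patient differently and each cite the protocol.

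Two things are at stake. The first is who may be enrolled, and who later counts as a major deviation: the per-protocol analysis in Section 9.5 keeps only patients who completed treatment, had the end-of-treatment biopsy and had no major deviation. The second is the handling of a serious clinical event. The hypoglycaemia rule is written as if a sulfonylurea were the only drug whose dose could be lowered, although the same section carries insulin forward and names insulin detemir for deteriorating control.

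**Working it through.** The protocol gives no figure to reproduce on this point, so the check is a comparison of the texts.

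**Step 1: entry.** Each background treatment is taken through the three sections.

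| Background treatment (type 2 diabetes) | 5.2 entry rule | 5.3 diabetes-specific exclusions | 5.4.3 |
|---|---|---|---|
| Diet only | admitted | not excluded | nothing to continue |
| Metformin and/or sulfonylurea, stable | admitted | not excluded | continued |
| Insulin | not admitted | not excluded | continued |
| DPP-IV inhibitor | not admitted | not excluded | continued |
| TZD, GLP-1-based, SGLT2 inhibitor | not admitted | excluded | not allowed |

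The sections agree in the first, second and last rows. They disagree in the insulin and DPP-IV rows, and Section 5.3 is silent exactly there, so it cannot break the tie.

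**Step 2: can timing explain it?** Section 5.2 applies at screening and 5.4.3 at randomisation, so in principle a drug could be added in between. Section 6 puts screening, enrolment, randomisation and baseline tests in "visits 1 and 2, over a maximum period of 14 days". Section 5.4.3 also speaks of previous treatment. A change within at most two weeks is not a plausible reason for the longer list.

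**Step 3: is the 5.4.3 list reliable as printed?** It classes insulin as an oral drug, which it is not. The list therefore contains a drafting error, and the text does not show whether the error lies in the word oral or in the inclusion of insulin.

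**Step 4: the hypoglycaemia rule, by background treatment.**

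| Treatment when recurrent major hypoglycaemia occurs | Branch in 5.4.3 | Insulin addressed? |
|---|---|---|
| Sulfonylurea, no insulin | sulfonylurea reduction | not applicable |
| Sulfonylurea and insulin | sulfonylurea reduction | no |
| Insulin, no sulfonylurea | discretionary withdrawal from trial treatment | no |
| Neither | discretionary withdrawal from trial treatment | not applicable |

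The third row follows from the bracketed gloss, which equates the absence of a sulfonylurea with the absence of any possible reduction. If the gloss were meant only as an example, an insulin user whose dose could be lowered would fall in neither branch. On both readings the rule leaves out a drug that the section permits.

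**Step 5: reach into the analysis.** A patient withdrawn from trial treatment has not completed it and leaves the per-protocol set (Section 9.5). In the primary analysis (Sections 9.2 and 9.3), the patient counts by the biopsy result if a week-72 biopsy is taken, and as a non-responder if it is missing.

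**Step 6: size.** Section 5.1 plans 52 patients. At 1:1 that is 52/2 = 26 per arm, so one reclassified patient is 1/26 = 3.8% of an arm, and two are 2/26 = 7.7%. The protocol gives neither the expected share with diabetes nor the share on insulin or DPP-IV inhibitors, so the number affected is unknown and could be zero.

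**The case against.** The strongest reply is that this is a wording gap with limited reach. The primary endpoint is histology, read centrally and blind. Withdrawal under the hypoglycaemia rule is discretionary, and a patient who stops treatment but has the final biopsy remains evaluable under Section 9.2. All of that stands, and it limits the consequences. It does not settle who is eligible, and an analysis plan cannot repair an entry criterion.

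Some stronger readings are tempting, but the protocol does not support them.

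- *Insulin users are automatically withdrawn.* They are not: the sentence leaves it to the chief investigator.
- *Insulin is frozen at its starting dose.* The same-dose wording describes continuation at randomisation. It covers sulfonylureas too, which the section then allows to be halved. Nothing forbids adjusting insulin.
- *DPP-IV inhibitors are a named rescue drug.* Only insulin detemir is named; they could come in at most under other allowed drugs. Nor does starting a drug after randomisation breach an entry criterion.
- *Injected insulin invalidates HOMA-IR, hepatic insulin extraction and related indices and biases the comparison of arms.* These indices are not among the Section 7 outcomes, and most belong to an optional substudy to be published separately. Any distortion depends on the assay detecting injected insulin, which the protocol does not say, and its size depends on how glucose and fatty acids move at the same time. The handling of insulin users in such indices is ordinary analysis-plan content. Limiting the indices to patients off insulin at both tests would also select on an event after randomisation, so it is not a remedy to adopt here.

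**Conclusion.** The contradiction is real and rests on the text alone. Sections 5.2 and 5.4.3 give opposite answers for patients taking insulin or DPP-IV inhibitors at entry, and 5.3 does not decide between them. Eligibility and per-protocol status for these patients are therefore undefined. Separately, the hypoglycaemia rule is incomplete for insulin users, although the section both continues insulin and names it for HbA1c above 9%.

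The finding needs no assumption about drug effects or assays. It does assume that the 5.2 list is exhaustive, which is its plain reading. The number of patients affected cannot be estimated from the protocol; at 26 per arm, each one is 3.8% of an arm in any set whose membership depends on the answer. No bias in the primary comparison is shown, and none is claimed.

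**What to change.** - Reconcile Sections 5.2, 5.3 and 5.4.3 so that a single list states which glucose-lowering drugs are permitted at entry and which during the trial. Correct the classing of insulin as an oral drug.
- Reconcile the rule for recurrent major hypoglycaemia with the insulin use that 5.4.3 permits, so that each permitted treatment combination falls in a defined branch.
- State whether a patient taking insulin or a DPP-IV inhibitor at entry counts as a major deviation for the per-protocol set in Section 9.5, and fix this before unblinding.

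Which drugs are permitted, and what the hypoglycaemia rule should contain, is for the sponsor to set. The cost is amendment wording and a check of the entry medication of patients already enrolled. Sample size and the primary analysis method do not change.

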5.5 Randomization, stratification and blinding

Randomization and stratification

Participants meeting all the eligibility criteria and providing written informed consent will be randomized centrally on a 1:1 basis to either of the two-study treatments (phytosomal curcumin vs placebo) using computer generated randomization. To ensure even distribution between groups in key baseline covariates, randomization will be stratified into blocks of 4 according to the following variables: diabetes status (present vs. absent), obesity status (present vs. absent), fibrosis stage (stage F3-4 vs. stage 0-2), CKD (present vs. absent). Trial participants will be allocated a unique trial identification number to preserve patient confidentiality and enable the study to be double-blinded. Patients, investigators, assessors, trial site staff, and the sponsor (except for specific laboratory staff and individuals responsible for safety) remained blinded to treatment assignment throughout the trial.

Medication preparation and blinding/unblinding procedures

Both active treatment (phytosomal curcumin) and placebo control will be packaged and labelled with a unique identification number (in keeping with the European Unions Good Manufacturing Practice for Medicinal Product guidelines) by the manufacturer (Indena S.p.A.), to the extent that the receiving trial site will be blinded to the study drug throughout the duration of the trial. Sealed parcels (containing electronic information) will be sent with each drug package for the attention of the unblinded members of the central trial management group (TMG) nominated statistician, RG and database programmer, EP, to ensure (1) safe delivery of the correct drug and (2) blinding of the treatment allocation from the remainder of the TMG and the trial patient. Unblinding of treatment will only take place if the identity of the allocated study medication will be necessary for patient safety and care. If a serious adverse event (SAE) is deemed unexpected and possibly, probably or definitely related to phytosomal curcumin (ie, suspected unexpected serious adverse reaction=SUSAR), a clinical member of the TMG was unblinded to the medication to evaluate causality and subsequently label the event either as an unrelated SAE (for patients receiving placebo) or a SUSAR (for patients receiving phytosomal curcumin). The latter will be reported to the MHRA and the NRES, and only if patient safety is jeopardised the study medication will be discontinued and the treating clinician/patient informed.

6. Trial schedule and data collection

The trial will involve nine patient-related visits at their nearest trial site (**Figure 1**).

The study comprises four stages: (1) screening, enrollment, randomisation and baseline investigations (visits 1 and 2, over a maximum period of 14 days), (2) 504 days of study treatment (visits 3–7, over 72 weeks), (3) primary endpoint assessment including liver biopsy (visit 8, within 1 day of the EOT) and (4) post-treatment follow-up assessment (visit 9, 12 weeks after EOT). If the trial investigating team or the trial participant suspected an AE, an unscheduled visit was arranged within 24 h. Each visit included patient interview, clinical examination, anthropometry and blood/urine chemistry.

The schedule for the study visits and data collection is summarised in **Figure 1**. All participants were asked to attend each visit under fasting from eating or drinking (with exception of water and due medications) for a minimum of 8 h prior to each visit. A follow-up liver biopsy (ie, primary endpoint)

was obtained under ultrasound-guidance after completion of the 72-week study treatment. Wherever possible, a 16-gauge biopsy needle and a specimen length of a minimum of 15 mm are preferred. The liver tissue will be prepared at the local trial site in preparation for histological assessment (under light microscopy) at the central trial site at HUMANITAS Gradenigo hospital. On receipt, the 'blinded' central histopathologist (RP) will record the size and quality of the histology slides. A minimum of four unstained slides were available for each liver biopsy to enable repeat staining (H&E, haematoxylin van Gieson, Ubiquitin) to ensure adequate quality for interpretation. Liver biopsy tissue specimens will be collected, paraffin-fixed and stored at the diagnostic archive of the Department of cellular pathology (HUMANITAS Gradenigo hospital). Fasting serum and plasma samples were collected at each of the 9 visits, will be partly used for routine biochemistry and partly stored frozen in 0.5–1.0 mL aliquots at –80°C at HUMANITAS Gradenigo Hospital. Additional blood (buffer coat) will be obtained at visits 1 and 8 for future DNA extraction and stored at –80°C.

Treatment compliance

Treatment compliance will be monitored at each visit by a review of the returned sealed envelopes and pill count.

Phytosomal Curcumin Trial Design: Randomised, multi-centre, double-blinded, placebo-controlled clinical trial

[figure not shown]

Figure 1 Schematic of phytosomal curcumin efficacy and action in non-alcoholic steatohepatitis trial design. Eligible participants are randomly assigned to a 72-week treatment of phytosomal curcumin 1 g daily or placebo control. Both the trial investigators and the participants are blinded to drug allocation.

Figure 1: schematic of the trial design.

7. Study outcome measures: primary and secondary outcomes, adverse events(AEs) reporting and analysis

Primary outcome measure

Histological NASH resolution (defined by the NASH Clinical Research Network as no more than mild residual inflammatory cells [score of 0 or 1] and no hepatocyte ballooning [score of 0]) **and** no worsening of liver fibrosis (with worsening defined as an increase of one stage or more on the Kleiner fibrosis classification scale) after 72 weeks, in line with regulatory perspectives^{31,32}.

Secondary outcome measures

Liver-centered histological outcomes:

1) a ≥ 1 stage improvement in fibrosis and no worsening of NASH (with worsening defined as an increase of ≥ 1 point in either the lobular inflammation score or the hepatocyte ballooning score according to the NASH Clinical Research Network criteria) after 72 weeks

2) improvement in clinically significant fibrosis³³, defined by the proportion of patients with baseline fibrosis stage ≥ 2 who have fibrosis stage 0-1 at EOT, without worsening of NASH.

3) improvement in advanced fibrosis, defined by the proportion of patients with baseline fibrosis stage 3-4 who have fibrosis stage 0-2 at EOT, without worsening of NASH.

3) a ≥ 2 -point improvement in NAFLD activity score (NAS), with at least 1 point improvement in either ballooning or lobular inflammation score;

4) individual components of the NAFLD activity score (steatosis, hepatocyte ballooning, lobular inflammation) and the Kleiner fibrosis stage. Fibrosis stages 1a, 1b, and 1c were considered stage 1 for the purposes of analysis.

Liver-centered non-histological outcomes:

4) changes from baseline to 72 weeks in serum liver enzyme concentrations, improvement in noninvasive markers of liver disease severity, including computerized sonographic hepato-renal ratio (which correlates closely with histologic and ¹H magnetic resonance spectroscopy steatosis^{34,35, 36,37,38}, see **Analytical**

Methods subheading), serum cytokeratin-18 fragments(a marker of NASH), NAFLD fibrosis score, FIB-4 and serum lumican (as markers of fibrosis)(see supplementary material).

The extracellular matrix proteoglycan lumican was chosen because its circulating levels have been shown to be a reliable marker not only of hepatic fibrosis but also of active hepatic fibrosis deposition, its expression is upregulated by Nf-kB, and its levels have been shown to differentiate histologically progressive, fibrosing NASH from mild, nonprogressive NAFLD^{39, 40, 41}

Non liver-centered outcomes

-Improvement in anthropometry, physical activity and dietary parameters (body weight, BMI, waist circumference), physical activity and daily dietary consumption.

-Improvement in glycaemic control (fasting plasma glucose, HbA1c)

-Improvement in cardiovascular risk profile: fasting plasma lipids, oxidative stress markers, inflammatory markers/adipokines and chemokine MCP-1.

-Chronic kidney disease (CKD) regression. CKD will be defined according to Kidney Disease Improving Global Outcomes (KDIGO) guidelines as sustained (i.e., documented on 2 occasions at least 3 months apart) reduction in estimated Glomerular Filtration Rate [eGFR] <60 mL/min/1.73 m² **and/or** sustained increase in albumin excretion rate (AER) ≥30 mg/d. CKD regression will be defined as sustained (i.e., documented 3 month apart, on both follow-up visit 7 and visit 8) estimated Glomerular Filtration Rate [eGFR] ≥60 mL/min/1.73 m² **and** normalization of AER (i.e., <30 mg/d).

eGFR will be assessed from serum creatinine using the **CKD-EPI** (Chronic Kidney Disease Epidemiology Collaboration) equation, as recommended by KDIGO guidelines⁴². eGFR and AER will be classified according to KDIGO categories⁴³

-Change in absolute values of eGFR^{44, Error! Bookmark not defined.}, and of albumin excretion rate(AER).

We will estimate mean annual rates of change in eGFR from baseline to the final follow-up visit (total slopes), within each treatment allocation using linear mixed model repeated measures (MMRM);

adjustments were made for age, baseline eGFR, baseline urinary AER, diabetes, baseline fibrosis stage, systolic blood pressure, angiotensin-converting enzyme/angiotensin receptor blocker⁴⁵(see. **supplementary material**)

Exploratory outcomes

We explored the effect of treatment on Nuclear Factor(NF)-kB activation in the liver and in circulating mononuclear cell(MNCs). NF-kB is a key proinflammatory transcription factor involved in NASH development and progression and a known molecular target of curcumin (see Methods and supplementary material).

Safety outcomes

Safety end points include adverse events after the start of treatment, biochemical assessments, and clinical assessments. Selected events (including deaths, cardiovascular events, and acute pancreatitis) were adjudicated by an independent, external event-adjudication committee, whose members were unaware of the treatment assignments. A complete list of the trial end points is provided in protocol Table 1.

AE reporting and analysis

The reporting period for AEs will start at screening visit 1 and will continue until follow-up visit 8. SAEs were reported until day 504 (week 72) of the trial treatment and for 84 days post-EOT. All SAEs and adverse reactions will be evaluated by the investigators and recorded. The National Cancer Institute's common terminology criteria for AEs (CTCAE, V.4.02, 2010) will be used to grade each AE.

An AE will be deemed serious if it results in hospitalization or a visit to the emergency room where an intervention is made to avert hospitalization. The nature and number of all serious adverse events was adjudicated by an independent data management committee (DMC) who is unaware of treatment assignment at the time of ascertainment.

The central trial office (CRCTU, Turin) will keep detailed records of all AEs reported (nature, onset, duration, severity, outcome) and perform an evaluation with respect to seriousness, causality and expectedness.

Interim analysis of safety data will be performed and presented to the independent data management committee (DMC) on a 6-monthly basis. The unblinded DMC advises accordingly with regards to the trial conduct and specifically whether extra/new data monitoring will be required for the remainder of the trial.

The DMC operated in accordance with a trial specific charter based on a predefined template.

8. Analytical Methods

